6.3.2 Off-Site SAE Reporting

When participating in multicenter clinical trials, Principal Investigators may receive “off-site” reports (e.g., SAE Report). These are Sponsor reports of SAEs which occurred at other sites for the same trial, or in different trials using the same test article, that met the criteria for reporting to a regulatory agency. These should be reported to the reviewing IRB per their established reporting procedures. The IRB may require a revision to the ICF and reconsenting of patients if the SAE provides new information regarding risk to the study subject.

6.3.3 Reporting of Complaints for Marketed STAAR Surgical Products

All information collected on a CRF could potentially be identified as a product complaint, as defined in Section 6.1.3. During clinical monitoring by the Sponsor/designee, the information collected on the CRFs will be evaluated to determine if any of the information should be forwarded to the Sponsor for consideration as a complaint according to STAAR standard operating

procedures (SOPs) for complaint handling. The Sponsor has the responsibility for evaluating and investigating potential complaints in accordance with STAAR's internal complaint handling procedures.

Any complaints, malfunctions or similar events related to ancillary STAAR Surgical marketed products used in this study should be reported by the Investigators in accordance with the reference information provided on the commercial packaging.

6.3.4 Adverse Events and SAEs at Subject Exit

Ongoing ocular AEs at study exit will be documented as such in the CRFs and followed per the Investigator's standard of care.

Ongoing SAEs and ADEs will be followed until resolution or no further change in the condition is expected. Non-serious AEs that are ongoing at the study exit visit or upon discontinuation from the study will be followed per the Investigator's standard of care. Documentation in the eCRF of this follow-up is not required although subject care should continue as appropriate.

7.0 STATISTICAL METHODS

7.1 Study Endpoint and Parameters

7.1.1 Primary Endpoints

Primary endpoints will be evaluated in primary eyes only.

- Incidence of PI required to treat elevated IOP caused by mechanical pupillary block through Postoperative Visit 5 (Day 147 – 182).

The prespecified safety and performance endpoint (SPE rate) for the first primary study endpoint is the rate of PI required to treat elevated IOP caused by mechanical pupillary block with the approved and currently marketed MICL and TMICL devices, which is approximately 0.3%.

The additional primary endpoints have no prespecified performance targets:

- Distribution of percent ECD losses and the percent of eyes that have ECD <1500 and ECD <1000 through Postoperative Visit 5 (Day 147 – 182).
- Incidence of AEs through Postoperative Visit 5 (Day 147 – 182).

7.1.2 Secondary Endpoints

Secondary endpoints will be evaluated in all eyes (primary and fellow eyes) using descriptive statistics with comparisons to PMA data for the approved and currently marketed MICL and TMICL devices, where appropriate. The secondary endpoints have no prespecified performance targets.

- Incidence of PI required to treat elevated IOP caused by mechanical pupillary block through Postoperative Visit 5 (Day 147 – 182).
- Distribution of percent ECD losses and the percent of eyes that have ECD <1500 and ECD <1000 through Postoperative Visit 5 (Day 147 – 182).
- Incidence of AEs through Postoperative Visit 5 (Day 147 – 182).

7.1.3 Additional Study Parameters

The following will also be assessed in this study:

- MRSE within ± 1.00 D of target at Postoperative Visit 5
- MRSE within ± 0.50 D of target at Postoperative Visit 5
- UDVA of 20/40 or better at Postoperative Visit 5 (for those eyes with CDVA 20/20 or better at Preoperative Visit)
- CDVA through Postoperative Visit 8 (Day 1050 – 1170)
- Distribution of percent ECD losses and the percent of eyes that have ECD <1500 and ECD <1000 through Postoperative Visit 8

There are no prespecified performance targets for the additional study parameters.

7.2 Sample Size

Based on complaint data, the event rate for secondary PI required to treat elevated IOP caused by mechanical pupillary block for the approved and currently marketed MICTL and TMICTL devices is approximately 0.3%. Following the recommended analysis in ISO 11979-7:2018, Annex E, for cumulative adverse events, the null hypothesis is that the true rate of PI required to treat elevated IOP caused by mechanical pupillary block is less than or equal to the SPE rate, and the alternative hypothesis is that the true rate of PI required to treat elevated IOP caused by mechanical pupillary block is greater than the SPE rate:

$$H_0 \text{ (null hypothesis): } \pi \leq 0.3\%$$

$$H_a \text{ (alternative hypothesis): } \pi > 0.3\%$$

where π is the observed rate of PI required to treat elevated IOP caused by mechanical pupillary block. Based on the analysis in ISO 11979-7:2018, Annex E, the maximum number of cases allowed before the SPE rate is exceeded for 300 primary eyes of 300 subjects is 3.

To allow for losses of 10% per year, a total of up to 333 primary eyes of up to 333 subjects will be enrolled.

In addition, in order to detect an AE with a true probability of occurrence among eyes of 1% with 95% probability, based on the binomial distribution, a sample of at least 300 eyes is required.

7.2.1 Sample Size Justification for a Bi-exponential Model of Endothelial Cell Loss

The fitting of a bi-exponential model involves estimating 4 parameters, named by SAS PROC NLIN, a, b, p, and q in the following model:

$$ECD = p \cdot \exp(-a \cdot \text{time}) + q \cdot \exp(-b \cdot \text{time})$$

Prior modeling submitted by STAAR from the MICL PAS study¹¹ was based on data from 169 subjects. Based on that sample size, the standard errors for the four model parameters are provided in the following table:

Parameter	Estimate	Approx Std Error
a	13.2593	44.9425
b	0.0208	0.00278
p	66.2263	33.6633
q	2591.8	22.8947

The sample size was then doubled to slightly over 338, which is a number close to the proposed sample size in this study, i.e., 300, in order to demonstrate the resulting increased precision. That doubling of the sample size yielded a reduction of the standard errors, as would be expected:

Parameter	Estimate	Approx Std Error
a	13.2593	31.7562
b	0.0208	0.00197
p	66.2263	23.7864
q	2591.8	16.1773

The doubling of the sample has the effect of reducing the standard error for each parameter by about 30%, as would be expected given that the reduction in the standard error is a function of the square root of N. Thus, the planned sample size of 300 in this study will allow more precise estimation of the curve than previously presented to the FDA in P030016/S022. Given the diminishing return from increasing the sample size further, we believe that 300 eyes will provide sufficient accuracy to model endothelial cell loss.

7.3 Analysis Populations

The safety analysis population will include all eyes implanted with an investigational EVO/EVO+ lens. Imputation of missing data will not be performed.

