3.2.3 Subject Discontinuation

A subject may be discontinued (at the discretion of the Investigator, the Sponsor and/or the IRB) prior to the final study visit for several reasons, including, but not limited to:

- voluntary withdrawal
- death
- surgical complication preventing implantation of the study lens in any eye
- explant of the study lenses

If both EVO/EVO+ study lenses are explanted, a minimum of one post-explant visit should be completed to record safety measures for the subject (e.g., CDVA, cataract/lens evaluation, endothelial cell count, etc.) prior to subject discontinuation.

Prior to discontinuing a subject, every effort should be made to contact the subject, schedule a final study visit, and obtain as much follow-up data as possible.

Adverse events will be followed as described in Section 6.0. Subject withdrawals will be documented clearly on the source document and applicable CRF.

Only subjects who do not receive any study lenses MAY be replaced. Subjects who are discontinued from the study following treatment will not be replaced.

Discontinued subjects should be followed outside of the study protocol according to the Investigator's normal postoperative standard of care.

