5.1.1 Preoperative Visit – Days -120 to Day -1

Prospective subjects who have provided informed consent will be screened to determine eligibility for implantation of study lenses in one or both eyes. Demographic information, relevant ocular medical history, and current ocular medication use will be collected. The preoperative clinical evaluation will consist of a complete ophthalmic examination conducted no more than 120 days prior to surgery. Determination of eligibility will include consideration of all inclusion and exclusion criteria, including preoperative ECD as measured by the central reading center, calculation of the appropriate spherical and cylindrical lens power and size as provided by the STAAR OCOS system, and the opportunity for prospective subjects to experience their correction in the event that postoperative cylindrical refractive error of ≥ 1 D is predicted.

Refer to Appendix A: Schedule of Visits and Parameters for assessments to be performed.

5.1.2 Operative Visit – Day 0

Subjects will be reassessed to confirm eligibility. In addition, any changes in concomitant medications or AEs will be recorded. If the subject no longer meets eligibility criteria, he/she will be considered a screen failure. If the subject is eligible, he/she will be enrolled in the study and undergo surgery according to the surgical procedure described in Appendix B. If the study lens is not implanted due to a surgical complication, the subject will be discontinued from the study.

At approximately 1-6 hours after surgery, an intraocular pressure (IOP) reading in the implanted eye will be conducted. Any complications, AEs, or associated treatment given will be appropriately documented and reported.

For subjects who qualify to participate bilaterally, fellow eye implantation will occur between 7 days and 14 days after uneventful surgery in the first eye. If, in an Investigator's medical judgment, second eye surgery should be postponed to a date more than 14 days from primary eye implantation due to a safety concern, the Medical Monitor's approval for second eye surgery will be required.

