7.4 Statistical Analysis

The first primary study endpoint is defined as the incidence of PI required to treat elevated IOP caused by mechanical pupillary block through Postoperative Visit 5. The primary analysis will be performed on a minimum of 300 primary eyes that have completed Postoperative Visit 5. Based on complaint data, the SPE rate for secondary PI required to treat elevated IOP caused by mechanical pupillary block is approximately 0.3% for MICTL/TMICTL. Based on the recommended analysis in ISO 11979-7:2018, Annex E, the maximum number of cases allowed before the SPE rate is exceeded for 300 primary eyes of 300 subjects is 3.

The other primary endpoints will be studied using the first treated (i.e., primary) eyes. Secondary endpoints and additional study parameters will be studied using all (primary and fellow) eyes. Data will be summarized with point estimates and exact binomial confidence intervals for binary outcomes such as MRSE within 0.50 D and 1.00 D of target and UDVA 20/40 or better. Continuous outcomes (e.g., %hex, CV) will be described with summary statistics to include N, mean, standard deviation, minimum and maximum, first and third quartiles, and median. Distributions, such as CDVA loss, trabecular pigmentation, PAS, AC cells and flare will be summarized by number and percentage for each visit.

ECD loss over the 1050 – 1170 days of follow up will be modeled using a bi-exponential model with adjustment for correlation between paired eyes. ECD and change in ECD will be summarized at each visit. The number and percentage of eyes with ECD < 1000 and < 1500 will be summarized over time using descriptive statistics.

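### Read most naturally, the plan counts AE incidence only in implanted eyes, so an eye whose implantation failed because of a surgical complication is recorded but not counted

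*Combined protocol and SAP*

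**What the plan says.** Section 7.1.1 lists as a primary endpoint, in primary eyes and without a performance target, "Incidence of AEs through Postoperative Visit 5". Section 7.3 names one population: "The safety analysis population will include all eyes implanted with an investigational EVO/EVO+ lens". It does not tie that population to any endpoint, and no enrolled or attempted-surgery population is defined. Section 7.4 says: "The other primary endpoints will be studied using the first treated (i.e., primary) eyes". The word treated is not defined.

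On the day of surgery (Section 5.1.2), a subject confirmed as eligible is enrolled first: "he/she will be enrolled in the study and undergo surgery". The plan foresees failure: "If the study lens is not implanted due to a surgical complication, the subject will be discontinued from the study". Section 3.2.3 lists the same situation among the reasons for discontinuation and adds: "Only subjects who do not receive any study lenses MAY be replaced". By contrast, "Subjects who are discontinued from the study following treatment will not be replaced".

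On recording, Section 5.1.2 requires: "Any complications, AEs, or associated treatment given will be appropriately documented and reported". Section 6.1.1 makes complications of phakic lens surgery reportable on the AE form. Section 6.3.1 asks for all serious AEs within 24 hours. Section 8.3 requires electronic case report forms for every enrolled eye. Section 6.0 and the adverse-event part of Appendix B, however, carry a parenthesis that confines ocular AEs to eyes with a study lens implanted.

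**The concern.** A failed implantation happens to a subject who is already enrolled, and the reason for the failure is itself an AE under Section 6.1.1. If treated means implanted, the analysis drops exactly those eyes whose surgery went wrong early enough to prevent implantation. Selection is then on the outcome being measured, and it acts in one direction. Where the subject is replaced, an implanted eye takes the vacant place, so the tables show no shortfall.

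At stake is a primary safety description that supports a premarket supplement. Section 6.1.2 counts untoward events arising from deployment of the device as adverse device effects, so the plan treats delivery of the lens as part of device safety. An incidence that omits failed deliveries does not fully match that definition. The overall AE rate would move little; an AE type seen only in failed implantations would appear as zero.

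**Working it through.** **Plan's own figure.** Section 7.2 says at least 300 eyes give 95% probability of seeing an AE with a true rate of 1%. 1 − 0.99^300 = 95.1%, and the smallest sufficient number is 299. The figure reproduces and is not in dispute.

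**Which eyes are counted.** Section 3.2.3 sets subjects discontinued after treatment, who are not replaced, against subjects who received no study lens, who may be. A subject whose only attempted implantation failed is in the second group. Treated therefore most naturally means implanted, which agrees with the single population in Section 7.3. A lens placed and later removed stays in the population and is not part of this gap.

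**Effect on the incidence of any AE.** Let x of N implanted eyes have an AE, and let k failed eyes, each with an AE, be added back:

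(x + k)/(N + k) − x/N = k(1 − x/N)/(N + k)

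This is positive for any rate below 100%. N is taken as 300 (minimum for the primary analysis) or 333 (planned enrolment). The documents give neither k nor an expected AE rate, so both are assumptions shown over a range. At k = 0 the effect is nil.

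| Implanted eyes with AE | k = 1 | k = 3 |
|---|---|---|
| 15/300 = 5.0% | 16/301 = 5.3% (+0.32 points) | 18/303 = 5.9% (+0.94) |
| 30/300 = 10.0% | 31/301 = 10.3% (+0.30) | 33/303 = 10.9% (+0.89) |
| 60/300 = 20.0% | 61/301 = 20.3% (+0.27) | 63/303 = 20.8% (+0.79) |
| 33/333 = 9.9% | 34/334 = 10.2% (+0.27) | 36/336 = 10.7% (+0.80) |

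Exact (Clopper-Pearson) 95% intervals for the second row are 6.85 to 13.97%, 7.11 to 14.30% and 7.62 to 14.95%. Every shift in the table lies within the interval of the planned estimate.

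**Effect on a single AE type.** Suppose a type occurs only in failed eyes. With 333 implanted eyes and every failure replaced, the plan shows 0/333. Counting attempted eyes gives 1/334 = 0.30% (0.01 to 1.66%) for one failure and 3/336 = 0.89% (0.18 to 2.59%) for three. Without replacement, three failures among 333 attempts give 0/330 as planned against 3/333 = 0.90% (0.19 to 2.61%). For an AE type that the failed eyes did not have, adding them back only enlarges the denominator and lowers that rate very slightly.

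**How likely the case is.** The chance of at least one failure in 333 attempts is 1 − (1 − p)^333. For assumed p of 0.1%, 0.3%, 0.5% and 1.0% this is 28%, 63%, 81% and 96%.

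**The case against.** The strongest reply is that exclusion is inferred, not stated. Section 7.3 is attached to no endpoint, the sentence governing the AE endpoint is in Section 7.4, and its key word is undefined. That stands: a reader might infer that the plan expressly excludes these eyes, and the documents do not go so far. They leave a term open for a primary endpoint, and the surrounding text points to implanted eyes.

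A reader might also infer that these complications go unrecorded. The documents do not support that. Sections 5.1.2, 6.1.1, 6.3.1 and 8.3 direct that they be captured, and Section 3.2.3 asks for follow-up data before discontinuation. The parenthesis in Section 6.0 and Appendix B may simply separate study eyes from an untreated fellow eye. Only a literal reading conflicts with Section 6.1.1, and only for non-serious events. The gap is in tabulation.

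It can also be said that implanted eyes are a coherent denominator for a study of the lens, and that failures should be few: investigators have prior experience with the lens family (Section 3.3), surgeons are certified (Appendix B), and a supplemental lens is supplied for each eye (Section 4.2). Both points are fair. The first supports keeping implanted eyes for the lens-dependent outcomes and showing them as a subset for AEs. The second bears on size, not on direction.

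**Conclusion.** The point holds in this form: on the most natural reading of Sections 7.3, 7.4 and 3.2.3, eyes with a failed implantation are recorded but not counted in the primary AE incidence, and the omission can only lower the incidence of any AE and of the AE types those eyes had. The size is about 0.3 percentage points per eye at about 300 eyes. This rests on treated meaning implanted and on each such eye having at least one AE, which follows from Section 6.1.1 when a surgical complication caused the failure. The number of such eyes is unknown and may be zero.

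It would be wrong to infer that the trial's one tested endpoint is biased. An eye without a study lens has no lens to cause pupillary block, so the iridotomy comparison with 0.3%, and its limit of 3 cases in 300 eyes, is essentially unaffected. The AE endpoint has no performance target, so no decision rule changes. The effect is probably small, and the case for acting is that the bias has a known direction and is cheap to remove.

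**What to change.** In Sections 7.3 and 7.4, define a set of all eyes in which study-lens surgery was started, fixing the starting point (for example, the first incision), and compute AE incidence over it with implanted eyes shown as a subset. State which set the term treated refers to for each endpoint. Keep implanted eyes for the iridotomy, ECD and refractive outcomes. Report the numbers of failed implantations and of replacements, and keep replaced subjects in the AE counts. As a minor accompanying point, reconcile the parenthesis in Section 6.0 and Appendix B with Section 6.1.1, so that non-serious surgical complications in attempted eyes are clearly within scope.

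The cost is wording in four places and an extra table row. The forms and operative-visit recording already exist, and the sample size and visit schedule do not change. The downside is a slightly less favourable AE rate, by about 0.3 points per such eye. A count and listing of failed implantations alone would make them visible, but would leave the incidence itself uncorrected.

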7.4 Statistical Analysis

The first primary study endpoint is defined as the incidence of PI required to treat elevated IOP caused by mechanical pupillary block through Postoperative Visit 5. The primary analysis will be performed on a minimum of 300 primary eyes that have completed Postoperative Visit 5. Based on complaint data, the SPE rate for secondary PI required to treat elevated IOP caused by mechanical pupillary block is approximately 0.3% for MICTL/TMICTL. Based on the recommended analysis in ISO 11979-7:2018, Annex E, the maximum number of cases allowed before the SPE rate is exceeded for 300 primary eyes of 300 subjects is 3.

The other primary endpoints will be studied using the first treated (i.e., primary) eyes. Secondary endpoints and additional study parameters will be studied using all (primary and fellow) eyes. Data will be summarized with point estimates and exact binomial confidence intervals for binary outcomes such as MRSE within 0.50 D and 1.00 D of target and UDVA 20/40 or better. Continuous outcomes (e.g., %hex, CV) will be described with summary statistics to include N, mean, standard deviation, minimum and maximum, first and third quartiles, and median. Distributions, such as CDVA loss, trabecular pigmentation, PAS, AC cells and flare will be summarized by number and percentage for each visit.

ECD loss over the 1050 – 1170 days of follow up will be modeled using a bi-exponential model with adjustment for correlation between paired eyes. ECD and change in ECD will be summarized at each visit. The number and percentage of eyes with ECD < 1000 and < 1500 will be summarized over time using descriptive statistics.

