3.0 STUDY DESIGN

3.1 Description of Study Design

This study will enroll and implant approximately 333 primary eyes and up to an additional 333 fellow eyes from subjects who qualify for bilateral implantation, at up to 20 clinical sites in the US. Postoperatively, subjects will return for visits at regularly scheduled intervals through

Postoperative Visit 8 (Day 1050 – 1170) as described in Appendix A. The analysis of the primary endpoint will be conducted after a minimum of 300 primary eyes complete Postoperative Visit 5 (Day 147 – 182) to support the Premarket Application (PMA Supplement P0930016/S035) of the investigational devices.

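### Section 7.4 and the synopsis analyse the tested pupillary-block endpoint on eyes that completed Visit 5, so a qualifying iridotomy in an eye that exits or misses that visit is, read literally, not counted.

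*Combined protocol and SAP*

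**What the plan says.** Section 7.4 defines the first primary endpoint as "the incidence of PI required to treat elevated IOP caused by mechanical pupillary block through Postoperative Visit 5". It then gives the eyes analysed: "The primary analysis will be performed on a minimum of 300 primary eyes that have completed Postoperative Visit 5". The statistical methods part of the synopsis repeats that sentence.

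Other places bear on which eyes count:

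- Section 3.1 (and the synopsis study design) uses the same 300 eyes for timing: the analysis "will be conducted after a minimum of 300 primary eyes complete Postoperative Visit 5".
- Section 7.1.1 limits the primary endpoints to primary eyes and sets no condition on completing a visit.
- Section 7.2 sets up the test "Following the recommended analysis in ISO 11979-7:2018, Annex E, for cumulative adverse events". The limit for 300 primary eyes is 3 cases. Enrolment is inflated: "To allow for losses of 10% per year, a total of up to 333 primary eyes".
- Section 7.3 names one population: "The safety analysis population will include all eyes implanted with an investigational EVO/EVO+ lens". It assigns no endpoint to it, and adds "Imputation of missing data will not be performed".
- Section 3.2.3 lists explant among the reasons for discontinuation and does not replace treated subjects who leave. Sections 5.1.4 and 5.1.5 provide for out-of-window and missed visits.

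**The concern.** The wording in 7.4 selects eyes by whether they completed a visit that comes after the event of interest. For a cumulative harm endpoint that is the wrong condition. An eye with a qualifying PI in its first weeks has already supplied its outcome, whatever happens at Day 147 to 182. If that eye later exits or has no in-window Visit 5, a literal reading removes a known event.

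An error in the numerator can run only one way. Leaving out event eyes lowers the count and favours the conclusion that the 0.3% rate is not exceeded. The limit is so small that one eye can decide the result. No sentence in the documents says that such an event stays in the count, or what the denominator then is.

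**Working it through.** **Inputs.** Target rate 0.3%, limit 3 in 300, 333 eyes enrolled, losses of 10% per year (section 7.2). Visit 5 closes at Day 182 (section 5.1). No significance level is stated. One-sided 5% is assumed, since the alternative in 7.2 is one-sided, and 2.5% is also checked.

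**1. The plan's limit.** The maximum allowed is the largest x for which P(X ≥ x+1) ≤ alpha, with X ~ Bin(n, 0.003).

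| n | P(X ≥ 3) | P(X ≥ 4) | Maximum allowed |
|---|---|---|---|
| 300 | 0.0626 | 0.0133 | 3 |
| 316 | 0.0707 | 0.0158 | 3 |
| 333 | 0.0798 | 0.0187 | 3 |

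The stated limit reproduces at both levels. It holds for every n from 274 to 456 at 5% and from 207 to 364 at 2.5%, so it holds across 300 to 333.

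**2. Planned loss by Visit 5.** 333 × (1 − 0.9^(182/365)) = 17.0 eyes (5.1%), leaving 316.

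**3. One event eye among the lost eyes.** Take 4 qualifying events in 333 implanted eyes, one of them in an eye that did not complete Visit 5.

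| Counting rule | Events/eyes | Rate | Exact one-sided p | Limit exceeded? |
|---|---|---|---|---|
| Literal completers | 3/316 | 0.95% | 0.071 | No |
| Completers plus event eyes | 4/317 | 1.26% | 0.016 | Yes |
| All implanted primary eyes | 4/333 | 1.20% | 0.019 | Yes |

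The conclusions are the same at 2.5%.

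**4. Expected effect.** Let d be the share of event eyes that do not complete Visit 5. Counted events follow Bin(333, p(1 − d)), and the limit is exceeded at 4 or more.

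| Setting | True rate 1% | True rate 2% |
|---|---|---|
| 333 eyes, d = 0 | 42.7% | 90.1% |
| 333 eyes, d = 5% | 39.0% | 87.8% |
| 316 eyes, loss unrelated to the event | 38.9% | 87.8% |
| Planned test, 300 eyes, no loss | 35.3% | 85.1% |
| 333 eyes, d = 25% (hypothetical) | 24.1% | 73.6% |

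The second and third rows agree to within 0.1 of a percentage point. At the planned loss rate the fall is therefore ordinary loss of sample size, and both figures stay above the planned 300-eye test. They fall below it only when d exceeds about 10% (9.9% at both true rates). The documents give no value for d.

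**The case against.** The strongest reply is that the 300 is a floor and merely repeats the trigger in section 3.1. The endpoint runs through Visit 5, the analysis cited in 7.2 is for cumulative adverse events, and the only defined population is all implanted eyes. On that view the sponsor already intends to count every event. This may well be so. But 3.1 says when the analysis is run, while 7.4 says which eyes it is run on, and nothing in 7.1, 7.2 or 7.3 overrides 7.4. The ISO annex is not reproduced, so whether it sets a counting rule cannot be checked.

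Second, an omitted event would not vanish. It would appear under "Incidence of AEs through Postoperative Visit 5" in primary eyes, and section 7.1.2 makes PI incidence in all eyes a secondary endpoint. A discrepancy would be visible. That stands and limits the harm, but neither endpoint has a target, so neither replaces the tested count.

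Third, the exit route is thin. Section 3.2.3 says subjects may be discontinued for explant, its post-explant rule concerns both lenses, and it asks for every effort to obtain a final visit. Nothing ties a PI to exit. That also stands.

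A reader might go further and infer that the plan is biased by a known amount, or that events will be dropped. The documents support neither. The fall from about 43% to 39% equals what non-selective loss produces, and bias beyond that needs event-related exit, for which no rate is given. Nor does the restriction lower the observed percentage in every case: leaving event-free lost eyes out of the denominator raises it slightly.

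**Conclusion.** The point holds as a conflict of wording that should be fixed before data are seen. Taken at its word, section 7.4 can drop a qualifying event from the only tested endpoint, always in the device's favour, and one omitted eye at 4 events reverses the conclusion. The expected effect is small. At the planned losses the chance of exceeding the limit stays above that of the 300-eye design, and it falls below only if more than about 10% of event eyes fail to complete Visit 5. These figures assume exact binomial testing at one-sided 5%, with the decisions unchanged at 2.5%, and a constant 10% yearly loss. The sample size and the limit of 3 are not in question.

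**What to change.** In section 7.4 and the synopsis, replace the sentence with text to this effect:

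- The analysis is run once at least 300 primary eyes have completed Visit 5.
- Every qualifying PI in an implanted primary eye through the Visit 5 window counts toward the limit, whether or not Visit 5 was completed.
- The denominator is the primary eyes that completed Visit 5 plus any primary eye with a qualifying PI before exit or a missed visit.

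This needs no imputation, so it agrees with section 7.3, and it keeps event-free eyes with unfinished follow-up out of the denominator. As a sensitivity analysis, report the rate over all implanted primary eyes, with the number of event-free eyes lost or not yet at Visit 5. That rate treats those eyes as non-events, which is why it should not be the main analysis.

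The cost is one replaced passage in two places and one extra table row, with no added subjects or visits. The limit stays at 3 for any denominator from 300 to 333. The downsides are that slightly more events may count against the device, and that adding event eyes to the completers slightly raises the observed rate (4/317 = 1.26% against 4/333 = 1.20% in the example).
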